6.3.7 Removal of subjects

Engagement with the study is voluntary. If a participant wishes to withdraw, they will stop using the NeuViCare AI software and not complete follow-up surveys.

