3.2.1 Potential Risks

This risks to human subjects in the proposed research are minimal. Specific Aim 1 involves qualitative interviews and a design thinking workshop with various stakeholders regarding the role of AI + care coaching during ED-to-home community care transitions. Specific Aim 2 involves the pilot testing of the NeuViCare AI. Psychologically, there is a risk that participants will find the interviews and engagement with the AI + care coach burdensome or distressing. There is also a risk of inadvertent release of potentially identifying information. Other physical, social, cultural, financial, and legal risks are minimal. Data collection, management, and analytic processes outlined in the proposal are designed to ensure that participant privacy and confidentiality will be maintained.

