5.2 Outcome Variables

5.2.1 Primary Outcome Variables

After in-ED enrollment, we will collect baseline measurements of PLWD and their care partners. Particularly, at time 0 this will include domain assessments of validated tools addressing dementia knowledge, PLWD self-efficacy, psychological well-being, social connectedness, and caregiver experience. After ED- or hospital-community care transition, a virtual session led by the care coach will build upon discharge instructions by developing a comprehensive transdisciplinary care plan and integrating the use of NeuViCare AI technology. Subsequent sessions with the PLWD and their care partner will assess knowledge translation of NeuviCare AI, follow through with care plan, and the development of sustainable skills for preventing crisis and recidivism. At follow-up time points of 7 days, 30 days, and 3 months, participants will be contacted to reassess responses to above domains of interest (primary outcome).

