6.2.3 Adverse Events Definition and Reporting

The PI will take all possible measures to minimize any risks that may occur as a consequence of participation in this investigation. Adverse events will be recorded and noted by the PI, and reported to the Yale University Human Research Protection Program. While we feel that such events are very unlikely, we will follow all until resolution if adverse events occur.

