6.3.6 End of Study and Follow-up

Participants will be assessed up to 3 months post-ED visit regarding outcomes through surveys built into the AI platform. There is no in-person follow-up.

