6.4 Statistical Method

6.4.1 Statistical Design

Recorded interviews will be professionally transcribed. We will perform coding throughout the study using a qualitative descriptive approach with thematic analysis. A draft code key will be generated through an inductive coding process. Interviews and coding will occur concurrently, and coding disagreements will be resolved by group consensus. We will use the final code key to analyze the remaining transcripts, and will then produce code reports and identify themes while maintaining an audit trail of coding decisions. NVivo, a specialized software package for qualitative research, will be used to facilitate data organization and theme identification.

Additionally, we will use a primarily inductive approach to content analysis whereby theoretical insights will be developed from the design thinking workshop data. Similar to prior qualitative work within design thinking workshops, themes and subthemes will be generated and grouped by common words, phrases, or ideas.

Regarding the DKAS and Zarit Caregiver burden scale, we will compare baseline and 30-day mean scores of the pilot group using the paired t-test. Given the proposal's pilot nature, descriptive statistics will be used to assess ED and hospitalization outcomes as well as survey data regarding implementation outcomes. A mean score of ≥ 4 using the FIM will be indicative of NeuviCare AI's feasibility. A mean score of ≥ 4 using the AIM will be indicative of NeuviCare AI's acceptability. A mean score of ≥ 4 (using the IAM will be indicative of NeuviCare AI's appropriateness. In analyzing usability data, the 10-item SUS has a possible original score of 0-40. After multiplication by 2.5 and conversion to a 0-100 scale, prior research suggests that above average usability are interventions with a score ≥ 68 .

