6.4.5 Handling of Missing Data

Missing data will be considered missing at random and will not be imputed.

7 Trial Administration

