7.5 Data Collection

Data will be collected using the NeuViCare AI app.

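### The only withdrawal rule ties stopping the app to stopping the surveys, so people who leave early because of burden drop out of later feasibility ratings and the 30-day burden comparison

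*Combined protocol and SAP*

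**What the plan says.** Section 6.3.7 is the only rule on removal of participants: "If a participant wishes to withdraw, they will stop using the NeuViCare AI software and not complete follow-up surveys". It describes one exit. It does not provide for stopping the software while still answering surveys, for a closing assessment, or for recording why the person left.

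The data route runs through the same software. Section 6.3.6 says "Participants will be assessed up to 3 months post-ED visit regarding outcomes through surveys built into the AI platform", with no in-person follow-up, and 7.5 says "Data will be collected using the NeuViCare AI app". Section 5.2.1 does say "At follow-up time points of 7 days, 30 days, and 3 months, participants will be contacted to reassess responses to above domains of interest", but it describes no route other than the app.

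On analysis, 6.4.1 sets the feasibility criterion: "A mean score of ≥ 4 using the FIM will be indicative of" feasibility. The same cut-off applies to AIM and IAM, and 68 is the SUS benchmark. Zarit burden is compared between baseline and 30 days by a paired t-test. Section 6.4.5 adds: "Missing data will be considered missing at random and will not be imputed".

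On risk, 3.2.1 states that "there is a risk that participants will find the interviews and engagement with the AI + care coach burdensome or distressing". Section 6.2.3 has the principal investigator record and report adverse events and says "we will follow all until resolution if adverse events occur".

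**The concern.** In a usability pilot, leaving because the tool is a burden is itself evidence about feasibility and acceptability. Under this plan it does not count as evidence. It appears only as an absent rating, and the mean is taken over those who remain. Nothing in 6.4.1 makes retention or withdrawal part of the judgement.

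The missing-at-random assumption is least credible for these people, because their reason for leaving is closely related to what AIM, IAM, FIM, SUS and Zarit measure. Reduced 30-day care partner burden is one of the Aim 2 hypotheses in 4.1. A paired test that loses the care partners for whom burden rose would tend to look better than the enrolled group's experience.

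There is a smaller gap on the safety side. The written procedure for handling distress in 7.6 is for Aim 1, and the safety sections 6.2.2 and 6.4.3.3 are marked not applicable. Since no reason for withdrawal is asked, distress behind a pilot withdrawal has no explicit route to the investigator.

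**Working it through.** The plan contains no figure to reproduce: 6.4.2 (sample size) is marked not applicable, and no dropout rate or score distribution is given. The check has two parts.

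**1. Who is lost, reading the sections together**

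- Leaves before a given survey: no rating from that survey (6.3.7), and no replacement value (6.4.5).
- Leaves before day 30: no 30-day Zarit score, so no pair for the t-test (6.4.1).
- Leaves after day 30: the Zarit pair already exists and stays in the analysis. Nothing in 6.3.7 deletes data already given.
- AIM, IAM, FIM and SUS: the plan does not say at which time point these are given, so who would be lost from those means cannot be settled.

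**2. How few exits matter (illustration)**

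From the plan: about 25 in the pilot (5.3.1) and a pass mark of 4 (6.4.1). Assumed: one rating per enrolled participant, items scored 1 to 5, withdrawers leave before rating, and the completer mean c and withdrawer mean m shown below.

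All-enrolled mean with w withdrawals = [(25 − w) × c + w × m] / 25.

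The mean falls below 4 once w/25 exceeds (c − 4)/(c − m).

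| c | m | Break-even fraction | Last passing case | First failing case |
|---|---|---|---|---|
| 4.1 | 2.5 | 0.1/1.6 = 6.25% | w = 1: (98.4 + 2.5)/25 = 4.04 | w = 2: (94.3 + 5)/25 = 3.97 |
| 4.2 | 2.5 | 0.2/1.7 = 11.8% | w = 2: (96.6 + 5)/25 = 4.06 | w = 3: (92.4 + 7.5)/25 = 3.996 |
| 4.3 | 2.5 | 0.3/1.8 = 16.7% | w = 4: (90.3 + 10)/25 = 4.01 | w = 5: (86 + 12.5)/25 = 3.94 |
| 4.1 | 3.0 | 0.1/1.1 = 9.1% | w = 2: (94.3 + 6)/25 = 4.01 | w = 3: (90.2 + 9)/25 = 3.97 |

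Varying the withdrawers' score over 1, 2 and 3:

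- c = 4.2, w = 3: 3.82, 3.94, 4.06.
- c = 4.2, w = 5: 3.56, 3.76, 3.96.
- c = 4.4, w = 5: 3.72, 3.92, 4.12.

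In every row the completers-only mean passes. Whether the all-enrolled mean also passes depends on the number of exits, the completers' margin above 4, and how low the withdrawers would have scored. For Zarit, the plan gives no expected change or standard deviation, so only the direction can be argued.

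**The case against.** The strongest reply is that 6.3.7 describes leaving a voluntary study, and a person who leaves is entitled to stop giving data. It does not say that someone who merely stops opening the app is withdrawn, and it does not mention the care coach. That is a fair reading. The tie between using the tool and giving data comes as much from 6.3.6 and 7.5 as from 6.3.7, so rewriting 6.3.7 alone would not be enough. But the plan still offers no intermediate choice and no route outside the app for a person who wants one.

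A reader might infer more than the text supports:

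- That anyone who withdraws vanishes from the feasibility, acceptability and burden results. The rule stops surveys not yet completed; earlier data remain.
- That withdrawers are removed from the record of distress. Sections 6.2.3 and 7.6 have adverse events recorded and followed to resolution with no exception for withdrawal, and 7.12 adds quarterly safety reviews. The gap is that no reason is asked.
- That two withdrawals always reverse the conclusion. That depends on the assumed scores, as the table shows.
- That healthcare use is lost as well. A chart review step is mentioned in 7.6 and 7.9, though the plan does not say how it applies to withdrawers.

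It is also fair that this is a one-arm pilot, that implementation outcomes are descriptive, and that the cut-offs are only indicative. This limits the stakes. Even so, those cut-offs are the only stated basis for calling the tool feasible, acceptable and appropriate. Finally, the missing-at-random assumption would be open to question even with a better exit rule, which is why the fix also covers the analysis.

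**Conclusion.** The point holds in a limited form. Anyone who leaves before a given survey because of burden contributes nothing to that survey's result, and anyone who leaves before day 30 contributes nothing to the burden test. With no imputation, no sensitivity analysis and no withdrawal criterion, the reported results can lean towards success.

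In a pilot of about 25, between 2 and 5 unrated withdrawals at an assumed score of 2.5 would bring an all-enrolled mean below 4 when completers average 4.1 to 4.3. With completers at 4.1 and withdrawers at 3.0, two withdrawals still pass. The actual bias cannot be sized, because the documents give no dropout rate, no expected scores and no timing for the implementation surveys. On safety, the finding is only that pilot distress leading to withdrawal has no explicit capture route. This should be corrected; it does not invalidate the design.

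**What to change.** **In 6.3.7**, record three choices separately at exit: stops the app, stops the coach sessions, or stops surveys and contact. Keep those who stop only the app or the coach on the 7-day, 30-day and 3-month surveys, offered by telephone or by a link outside the app; amend 6.3.6 and 7.5 to allow this. At any exit, record the date and reason and offer a brief, voluntary closing rating (AIM, IAM and FIM, plus Zarit if before day 30). Pass any reported distress to the principal investigator for assessment under 6.2.3. An answer that the tool was burdensome should not be logged automatically as an adverse event.

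**In 6.4.1**, state when AIM, IAM, FIM and SUS are given. Report the number withdrawn, with reasons, out of all enrolled beside each mean. Add a sensitivity analysis showing whether each AIM, IAM and FIM mean stays at 4 or above when withdrawers without a rating are given a range of low scores, for example 1 to 3.

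**Cost:** a paragraph in 6.3.7, small edits to 6.3.6, 7.5 and 6.4.1, a short exit form that existing staff can use, and a consent-wording amendment. The downsides are an optional contact that some people leaving will decline, and a feasibility statement that may be less favourable.

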6.4 Statistical Method

6.4.1 Statistical Design

Recorded interviews will be professionally transcribed. We will perform coding throughout the study using a qualitative descriptive approach with thematic analysis. A draft code key will be generated through an inductive coding process. Interviews and coding will occur concurrently, and coding disagreements will be resolved by group consensus. We will use the final code key to analyze the remaining transcripts, and will then produce code reports and identify themes while maintaining an audit trail of coding decisions. NVivo, a specialized software package for qualitative research, will be used to facilitate data organization and theme identification.

Additionally, we will use a primarily inductive approach to content analysis whereby theoretical insights will be developed from the design thinking workshop data. Similar to prior qualitative work within design thinking workshops, themes and subthemes will be generated and grouped by common words, phrases, or ideas.

Regarding the DKAS and Zarit Caregiver burden scale, we will compare baseline and 30-day mean scores of the pilot group using the paired t-test. Given the proposal's pilot nature, descriptive statistics will be used to assess ED and hospitalization outcomes as well as survey data regarding implementation outcomes. A mean score of ≥ 4 using the FIM will be indicative of NeuviCare AI's feasibility. A mean score of ≥ 4 using the AIM will be indicative of NeuviCare AI's acceptability. A mean score of ≥ 4 (using the IAM will be indicative of NeuviCare AI's appropriateness. In analyzing usability data, the 10-item SUS has a possible original score of 0-40. After multiplication by 2.5 and conversion to a 0-100 scale, prior research suggests that above average usability are interventions with a score ≥ 68 .

6.4.2 Sample Size Considerations

N/A

6.4.3 Planned Analysis

6.4.3.1 Primary Analyses

See 6.4.1.

6.4.3.2 Secondary Objectives Analyses

See 6.4.1.

6.4.3.3 Safety

N/A

6.4.3.4 Analysis of Subject Characteristics

We will present descriptive characteristics of cognition screening (to identify degree of ADRD), health literacy, chronic conditions, sociodemographic factors, and ED chief complaint.

6.4.3.5 Interim Analysis (if applicable)

N/A

6.4.3.6 Health economic evaluation

N/A

6.4.3.7 Other

N/A

6.4.4 Subsets and Covariates

N/A

6.4.5 Handling of Missing Data

Missing data will be considered missing at random and will not be imputed.

7 Trial Administration

7.1 Ethical Considerations: Informed Consent/Accent and HIPAA Authorization

Information sheets will be Institutional Review Board (IRB)-approved and the participant/legally authorized representative (LAR)/surrogate decision-maker will have the document read to them. The RA will explain the research study to the participant and answer any questions that may arise. This conversation will take place in a private room or via telephone if the caregiver is not present in the ED.

Participants/LAR/surrogate decision-makers will have the opportunity to carefully review the information sheet and ask questions. The participants/LAR should have the opportunity to discuss the study with their family or surrogates, or think about it prior to agreeing to participate. Participants/LAR must be informed that participation is voluntary and that they may withdraw from the study at any time, without prejudice. A copy of information sheet will be given to the participants/LAR/surrogate decision-makers for their records.

See additional information in 6.3.2.

7.2 Institutional Review Board (IRB) Review

The protocol will be submitted to the IRB for review and approval. Approval of the protocol must be obtained before initiating any research activity. Any change to the protocol or study team will require an approved IRB amendment before implementation. The IRB will determine whether informed consent and HIPAA authorization are required.

A study closure report will be submitted to the IRB after all research activities have been completed.

7.3 Subject Confidentiality

Participant confidentiality and privacy is strictly held in trust by the participating investigators, their staff, and the sponsor(s) and their interventions. Therefore, the study protocol, documentation, data, and all other information generated will be held in strict confidence. No information concerning the study or the data will be released to any unauthorized third party without prior written approval of the sponsor.

All research activities will be conducted in as private a setting as possible.

The study monitor, representatives of the Institutional Review Board (IRB), or regulatory agencies may inspect all documents and records required to be maintained by the investigator, including but not limited to, medical records (office, clinic, or hospital) for the participants in this study. The clinical study site will permit access to such records.

The study participant's contact information will be securely stored at each clinical site for internal use during the study. At the end of the study, all records will continue to be kept in a secure location for as long a period as dictated by the reviewing IRB, Institutional policies, or, if applicable, sponsor requirements.

Study participant research data, which is for purposes of statistical analysis and scientific reporting, will be transmitted to and stored at the [insert location]. This will not include the participant's contact or identifying information. Rather, individual participants and their research data will be identified by a unique study identification number. The study data entry and study management systems used will be secured and password protected. At the end of the study, all study databases will be de-identified and archived at the Yale School of Medicine.

7.4 Deviations/Unanticipated Problems

A protocol deviation is any noncompliance with the study protocol. The noncompliance may be either on the part of the participant, the investigator, or the study site staff. As a result of deviations, corrective actions are to be developed by the site and implemented promptly.

It is the responsibility of the site investigator to identify and report deviations within 5 working days of identification of the protocol deviation. All deviations must be addressed in study source documents, reported to the study sponsor, and the reviewing Institutional Review Board (IRB) per their policies.

Unanticipated problems involving risks to participants or others include, in general, any incident, experience, or outcome that meets all of the following criteria:

- Unexpected in terms of nature, severity, or frequency given (a) the research procedures that are described in the protocol-related documents, such as the Institutional Review Board (IRB)-approved research protocol and informed consent document; and (b) the characteristics of the participant population being studied;
- Related or possibly related to participation in the research ("possibly related" means there is a reasonable possibility that the incident, experience, or outcome may have been caused by the procedures involved in the research); and
- Suggests that the research places participants or others at a greater risk of harm (including physical, psychological, economic, or social harm) than was previously known or recognized.

The investigator will report unanticipated problems (UPs) to the reviewing Institutional Review Board (IRB) and to the study sponsor. The UP report will include the following information:

- Protocol identifying information: protocol title and number, PI's name, and the IRB project number;
- A detailed description of the event, incident, experience, or outcome;
- An explanation of the basis for determining that the event, incident, experience, or outcome represents an UP;
- A description of any changes to the protocol or other corrective actions that have been taken or are proposed in response to the UP.

To satisfy the requirement for prompt reporting, UPs will be reported using the following timeline:

- UPs that are serious adverse events (SAEs) will be reported to the IRB and study sponsor, if applicable within 5 days in accordance with of the investigator becoming aware of the event.
- Any other UP will be reported to the IRB and study sponsor within 10 days of the investigator becoming aware of the problem.
- All UPs should be reported to appropriate institutional officials (as required by an institution's written reporting procedures), the supporting agency head (or designee), and the Office for Human Research Protections (OHRP) within & 10 days of the IRB's receipt of the report of the problem from the investigator.

7.5 Data Collection

Data will be collected using the NeuViCare AI app.

7.6 Data Quality Assurance

Participant Safeguards: For Specific Aim 1, telephone qualitative interviews and cognitive debriefing processes will be conducted by personnel with interview experience among PLWD and their care partners. In the unlikely event that a participant experiences distress, study personnel will be instructed to terminate the interview, listen to the concerns of the participants, and provide reflective statements so that the participant knows that his or her concerns were heard. Such events will also be documented by [name] as part of the audit trail standard in qualitative research.

NeuViCare AI: The application is implemented on the HIPAA compliant Google Compute Platform (GCP), also called Google Cloud. Hence, NeuViCare's computing, network, and data storage services are all on the cloud. All data collected and stored by the NeuViCare application is guaranteed to be only stored on the Cloud, encrypted at rest. For more information, you can visit the following website:

<https://cloud.google.com/security/compliance/hipaa-compliance/>. Amicus Brain has secured HIPAA Business Associate Agreement (BAA) from Google; thus, ensuring that all parties maintain HIPAA security and overall HIPAA compliance. Additional data safety measures include the following:

- Use of HTTPS 128-bit encryption for all data transfers using Secure Socket Layer transmission
- All data stored in Google Cloud is encrypted at the storage level using AES256 (a 256-bit key) file encryption
- Ensuring study data is only accessible to authorized users
- Using only servers in a secure private, HIPAA-compliant cloud environment provisioned from GCP
- Amicus Brain has instituted physical safeguards and cyber security safeguards including separation of environments and separation of roles to protect the Production cloud environment where the NeuViCare application is hosted.

Confidentiality and Data Safeguards: To minimize the risks to data confidentiality, data will be stored and accessed on secure servers, and access will be limited to members of the research team. For the step involving chart review, minimal personnel will be used, and no sections of the chart will be printed. Once variables that require access to protected health information have been constructed, a deidentified data set will be created for analysis, with each participant assigned a unique random number. Additionally, recorded interviews will not contain any identifying information. Access to the deidentified data set and qualitative interview transcripts will be limited and maintained on password protected computer systems in locked offices.

Adverse Events: The PI will take all possible measures to minimize any risks that may occur as a consequence of participation in this investigation. Adverse events will be recorded and noted by the PI, and reported to the Yale University Human Research Protection Program. While we feel that such events are very unlikely, we will follow all until resolution if adverse events occur.

